6.5.1 Prohibited Medications

The following medications are prohibited during the study:

- Psychotropic medications other than stable dose of an SSRI medication, or stable dose of a TCA medication;
- Subjects using beta-blockers.

Use of prohibited medications during the study will be captured as protocol deviations and discussed with the sponsor.

6.5.2 Allowed Medications

All medications are permitted, with the exception of those listed in Section 6.5.1.

6.6 Concomitant Therapies

Any concomitant therapy (occupational therapy, physical therapy, vestibular therapy, visual therapy, cognitive behavioral therapy, acupuncture, chiropractor, and/or other therapies) that the subject is receiving or receives during the study must be recorded on the eCRF along with:

- Reason for use;
- Dates of therapy including start and end dates.

6.7 Lifestyle and Dietary Study Restrictions

The following lifestyle and dietary restrictions should be followed during the study:

- **Physical Exercise:** Subjects must be willing to exercise or stretch for 20 minutes each day, while wearing the wrist-worn HR monitoring device (Waveband®), by following the directions provided by the ClearPlay© mobile application. Outside of this, subjects should not engage in any exercise during the 8-week study period that will make them short of breath.
- **Smoking:** Subjects must be willing to refrain from smoking for 1 hour prior to their daily exercise or stretching sessions.
- **Alcohol:** Subjects must be willing to refrain from drinking alcohol for 1 hour prior to their daily exercise or stretching sessions.
- **Dietary:** Subjects must be willing to refrain from consuming caffeinated or sugary beverages that may impact HR for 1 hour prior to their daily exercise or stretching sessions.

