5.3 Withdrawal and Replacement of Subjects

5.3.1 Reasons for Withdrawal of Subjects

Subjects will be informed that they have the right to withdraw from the study at any time for any reason, without prejudice to their medical care. The investigator also has the right to withdraw subjects from the study for any of the following reasons:

- Subject non-adherence to therapeutic intervention or protocol requirements. Please refer to Section 6.5 for lifestyle and dietary study restrictions. Subjects must also be able to upload data via the ClearPlay© mobile application daily. Failure to do so for 3 consecutive days will trigger a call from the site. Subjects who do not upload data for 5 consecutive days are to be contacted by the site again. Subjects who do not upload for 7 consecutive days are to be withdrawn from the study for poor compliance;
- Subjects from either group who exercise at a rate that exceeds that which is prescribed, as identified by either self-report (the Godin Leisure Time Exercise questionnaire) or by autonomic monitoring (using ClearPlay©) will be withdrawn from the study and coded as “lost to follow up”.
- Subject unwillingness to continue in the study;
- Any other reason based upon the medical judgment of the investigator.

The reason for study withdrawal is to be documented in the subject’s source documents and electronic case report form (eCRF).

At the time of discontinuation from the study, subjects are to have all the assessments planned for the follow-up visits performed after the last study drug dose, if feasible.

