5.3.2 Handling of Withdrawals or Early Termination of Subjects

Withdrawals or early termination: If a subject is withdrawn from the study for any reason, whether related to the study drug or not, or if a subject voluntarily withdraws, such subject will be considered an early termination subject. The investigator will make every effort to ensure that early-termination subjects complete an Early Termination visit.

Lost to follow-up: Reasonable efforts will be made to contact subjects who are lost to follow-up. These efforts must be documented in the subject's file.

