6 THERAPEUTIC INTERVENTION

6.1 Therapeutic Interventions Administered

The therapeutic intervention (graded exercise) to be used in this study is delivered through the ClearPlay© application. This application will be preloaded on the i-touch or i-phone device, which will be supplied to each eligible subject during the Baseline Visit. ClearPlay© provides the subject with a graded exercise program or passive stretching, which is used in conjunction with a wrist-worn HR monitoring device (Waveband®).²⁹

Each subject will cease their assigned Therapeutic Intervention when they have reach three consecutive days of PCSS score that is less than or equalled to the subject's pre-mTBI PCSS score. All subjects will be required to complete the Follow Up, Day 56 Visit, regardless of the date they cease Therapeutic Intervention.

Table 2: Therapeutic Interventions

Therapeutic Intervention	Description	Duration	Frequency
Telemetry-based graded exercise	Sub-symptom threshold aerobic exercise	20 minutes	Daily for 8 weeks
Passive stretching	Passive stretching	20 minutes	Daily for 8 weeks

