6.2 Therapeutic Intervention Components

ClearPlay© Application: The downloadable app will be available from the app store. The app has 4 components: connectivity with the Waveband® to transmit physiologic (HRV) data remotely; a fillable version of the PCSS; and a fillable version of the Godin leisure-time exercise questionnaire; an instrument for communication of AEs.

Waveband®: Each subject will be fitted with a Waveband® (fit-bit like device to remotely detect HR and HRV). This is to be worn while the subject completes the graded exercise program or passive stretching program.

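### Section 5.3.1 does not exempt subjects who stopped therapy on recovery, so one who resumes sport can be withdrawn before Day 56 and coded lost to follow-up

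*Protocol*

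**What the plan says.** Four parts of the protocol bear on a subject who recovers before Day 56.

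- **Stopping therapy (6.1).** "Each subject will cease their assigned Therapeutic Intervention when they have reach three consecutive days of PCSS score" at or below the pre-injury level. The visit schedule is unaffected: "All subjects will be required to complete the Follow Up, Day 56 Visit, regardless of the date they cease Therapeutic Intervention".
- **Activity limit (6.7).** Beyond the daily session, "Outside of this, subjects should not engage in any exercise during the 8-week study period that will make them short of breath". There is no release for subjects who have stopped therapy.
- **Withdrawal (5.3.1).** Two grounds are relevant. The first, which the investigator may use, is "Subject non-adherence to therapeutic intervention or protocol requirements. Please refer to Section 6.5 for lifestyle and dietary study restrictions". The second covers "Subjects from either group who exercise at a rate that exceeds that which is prescribed", found by the Godin questionnaire or by ClearPlay monitoring. These subjects are to be withdrawn and coded as lost to follow-up. Neither ground mentions the 6.1 stop.
- **Assessments on leaving (5.3.1, 5.3.2).** At discontinuation, "subjects are to have all the assessments planned for the follow-up visits performed after the last study drug dose, if feasible". In addition, "The investigator will make every effort to ensure that early-termination subjects complete an Early Termination visit". The Follow-Up/ET column of Table 5 includes the BCBT.

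Table 1 lists a secondary endpoint that compares BCBT measurements at entry with those at Day 56, and another that correlates them with symptom resolution.

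**The concern.** Section 6.1 keeps a recovered subject in the study to Day 56, while 5.3.1 can take the same subject out for doing what recovered people often do, which is return to sport. The protocol does not say which section governs.

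Withdrawal by this route would depend on having recovered, and recovery is the trial's outcome. What is at stake is mainly the Day 56 BCBT. It may be missing, or be taken early at a termination visit, in a subgroup defined by outcome. Planned adverse event collection to Day 56 would also be cut short for these subjects.

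The code is a second problem. Section 5.3.2 treats loss to follow-up as a matter of failed contact. A subject removed for exercising is reachable, so the code would misstate the discontinuation reasons that 9.4 tabulates.

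**Working it through.** The protocol gives no figure for withdrawals after recovery, so there is none to reproduce. The check compares the rules, with one count for scale.

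**1. Does the 6.7 limit end at recovery?** No. It is stated for the 8-week period. A recovered subject who plays sport hard enough to become breathless is in breach, on or off therapy.

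**2. Does the over-exercise ground reach that subject?** The text leaves it open. The trigger is a rate above the prescribed one, and after the 6.1 stop no session is prescribed. Either any exercise exceeds a prescription of none, or the ground has lapsed. The bullet gives no end point. Where it applies, its wording is mandatory, although the sentence that introduces the list speaks only of the investigator's right to withdraw.

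**3. Does the non-adherence ground reach that subject?** Yes, at the investigator's discretion. It covers breach of protocol requirements, points to the lifestyle restrictions, and needs no prescribed rate.

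**4. Would resumed sport be noticed?** It could be. The Godin questionnaire is weekly through the therapy period and is repeated at Day 56. Monitoring by Waveband would add little once sessions stop, since under 6.2 "This is to be worn while the subject completes the graded exercise program or passive stretching program".

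**5. What happens to the BCBT?** If the subject attends an Early Termination visit, a BCBT is done, but before Day 56. If not, there is no second BCBT, and 9.8 does not impute by default.

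**6. How many subjects could come under the unclear rule?** Inputs from 9.1: 200 per arm, with resolution assumed at 93% (exercise) and 80% (stretching).

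- Exercise: 0.93 × 200 = 186
- Stretching: 0.80 × 200 = 160
- Total: 186 + 160 = 346, and 346 / 400 = 86.5%

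This is before attrition. Section 9.6 defines resolution as three days strictly below the pre-injury score, while 6.1 stops therapy at or below it. Everyone who resolves therefore also meets the 6.1 stop, and 346 is a floor for that group at the planning rates. Each 1% of the 346 who were withdrawn would be about 3.5 subjects (0.01 × 346 = 3.46) without a BCBT at the true Day 56. The protocol does not give the shares who would resume sport, be detected, be withdrawn and miss the termination visit, so the calculation stops here.

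**7. Is the primary outcome affected?** Largely not, because a subject with three days strictly below the pre-injury score has already had the event. The exception is a subject who stops therapy with scores equal to the pre-injury score. That subject has met the stop but not the endpoint, and could be censored by withdrawal.

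**The case against.** The case for leaving the text alone is reasonable. The over-exercise ground most naturally lapses once nothing is prescribed, and the other ground is only a right to withdraw. Section 6.1 speaks directly to subjects who stop early and keeps them to Day 56. A loss needs a chain: breathless sport, detection, a decision to withdraw, then a missed termination visit. Even then 9.8 keeps all data up to withdrawal. Section 5.3.1 also requires the reason for withdrawal in the source documents and eCRF, so the true reason may be on record beside the code.

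Most of this stands, and it is why the point is minor. It does not settle the matter, because a site that applies 5.3.1 literally can still withdraw a subject whom 6.1 says must stay, and the mandated code is wrong for that subject.

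A reader might infer three stronger claims that the document does not support.

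- **That 6.7 is silent on how long the limit lasts.** It states the 8-week period. What it lacks is an exception for recovered subjects, and whether to grant one is a clinical choice.
- **That the Day 56 BCBT is lost for these subjects.** The termination visit includes the test, so the result may be an early value and not a missing one.
- **That the physiologic comparison is biased by a known amount or in a known direction.** Any such figure would need assumed loss shares, and nothing in the protocol links symptom resolution to BCBT normalization numerically.

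The reference in 5.3.1 to Section 6.5 should read 6.7. That is a clerical slip, since the sentence names the restrictions it means.

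**Conclusion.** The point holds and is minor. Section 5.3.1 has no exemption for subjects who stopped therapy under 6.1, and the 6.7 limit runs for the full 8 weeks. A recovered subject who resumes sport can therefore be withdrawn before Day 56, contrary to 6.1, and be coded lost to follow-up although reachable.

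The consequence is mainly outcome-related loss, or early timing, of the secondary Day 0 versus Day 56 BCBT, partly mitigated by the Early Termination visit. At least 346 of 400 subjects would meet the 6.1 stop if the 9.1 rates held and before attrition. How many would be withdrawn, and any effect on the arm comparison, cannot be estimated from the document. The conclusion rests on sites reading either 5.3.1 ground as still in force after therapy stops, which the text permits but does not require.

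**What to change.** In 5.3.1:

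- Limit over-exercise withdrawal to the period on assigned therapy.
- State that subjects who met the 6.1 stop are not withdrawn for exercising, under either ground, and stay in follow-up to Day 56. Record any breach of 6.7 by them as a protocol deviation.
- Code any over-exercise withdrawal by its true reason in place of lost to follow-up.
- Correct the cross-reference from 6.5 to 6.7 in the same edit.

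Whether the 6.7 limit should itself be relaxed after recovery is for the sponsor and investigators to decide on clinical grounds. The fix works either way.

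The cost is a few lines of protocol text and the matching disposition code, with no extra visits. The downside is that some Day 56 BCBT results will reflect activity resumed after recovery.

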7 STUDY ASSESSMENTS AND SCHEDULES

7.1 Safety Assessments

Refer to the Schedule of Events (Table 5) for the timing of all safety assessments.

7.1.1 Baseline Demographics

Subject demographics will be recorded, including date of birth, gender, race, ethnicity, alcohol history, drug/tobacco history.

7.1.2 Medical and Medication History

A detailed history of the head injury will be taken.

A complete medical history will be collected, not limited to but including evaluation for past or present neurological, cardiovascular, metabolic or pulmonary conditions, history of migraines, psychiatric history.

A detailed record of the head injury will be collected. Review of computed tomography (CT) scans or magnetic resonance imaging (MRI)s to be performed if applicable.

A review of prior medications will be completed. Prior medications are those used within 7 days of Screening.

7.1.3 Body Weight and Height

Body weight (in kg) (wearing light clothes, no shoes) and height (in cm) will be measured to allow the calculation of body mass index (rounded to 1 decimal place). *Note: Height will only be captured at the screening visit.*

7.1.4 Vital Signs including Beat to Beat Blood Pressure

Vital signs will be collected via a third-party FDA approved device (Caretaker4®).³⁰ The subject will be fitted with the Caretaker4® device which attaches to right arm and right finger and measures continuous beat to beat HR and BP. Once connected, 2 minutes of baseline data collection will occur, followed by 2 minutes of ice bucket (or ClearHeart©) data collection, and a further 2 minutes post-ice bucket data collection.

The investigator (or a qualified observer at the investigational site) will interpret the vital signs using one of the following categories: within normal limits, abnormal but not clinically significant, or abnormal and clinically significant (reported with corresponding AE).

7.1.5 Adverse Events

The categorization of AEs by seriousness, relationship and expectedness is summarized in Table 3, and forms the basis for understanding the reporting requirements of events.

Table 3: Categories of Adverse Events

Event Seriousness	Event Relationship and Expectedness			
	Not Related	Related		
Non-serious	Adverse event	Adverse event		
Serious	Serious adverse event	Serious Adverse Event		
		
 
 Expected	Unexpected	
 
 Serious Adverse Event	Suspected Unexpected Serious Adverse Reaction)	
 
	Expected	Unexpected
Expected	Unexpected			
Serious Adverse Event	Suspected Unexpected Serious Adverse Reaction)			

Unanticipated problems relating to the therapeutic intervention, involving risks to subjects and others will be monitored throughout the study.

7.1.5.1 Definition of Adverse Events

An AE is defined as any untoward medical occurrence in a clinical study subject. An AE can therefore be any unfavorable and unintended sign (including an abnormal laboratory finding), symptom, or disease. This includes an exacerbation of pre-existing conditions or events, intercurrent illnesses or the significant worsening of the indication under investigation that is not recorded elsewhere in the eCRF under specific efficacy assessments. Anticipated fluctuations of pre-existing conditions, including the disease under study that do not represent a clinically significant exacerbation or worsening need not be considered AEs.

It is the responsibility of the investigator to document all AEs that occur during the study. AEs should be reported on the appropriate page of the eCRF.

7.1.5.2 Adverse Device Effect

An ADE is an AE related to the use of an investigational medical device.

This definition includes:

- Adverse events with a relationship to the use of the investigational medical device;
- Adverse events resulting from insufficient or inadequate instructions for use, deployment, implantation, installation or operation, or any malfunction of the investigational medical device;
- Any event resulting from use error or from intentional misuse of the investigational medical device.

7.1.5.3 Definition of Serious Adverse Events

A serious adverse event (SAE) is any untoward medical occurrence that at any dose:

- Results in death;
- Is life threatening (ie, the subject is at immediate risk of death at the time the event occurred; it does not refer to an event which might hypothetically have caused death had it been more severe);

- Requires in-patient hospitalization or prolongation of existing hospitalization;
- Results in persistent or significant disability/incapacity;
- Is a congenital anomaly/birth defect;
- Is a medically important event or reaction.

Medical and scientific judgment should be exercised in deciding whether reporting is appropriate in other situations, such as important medical events that may not be immediately life threatening or result in death or hospitalization but may jeopardize the subject or may require medical or surgical intervention to prevent one of the other outcomes listed in the above definition. These should also usually be considered serious. Examples of such medical events include allergic bronchospasm requiring intensive treatment in an emergency room or at home, blood dyscrasias or convulsions that do not result in hospitalizations, or the development of drug dependency or drug abuse.

The following hospitalizations/admissions do not need to be reported as SAEs:

- Hospitalization for social reason (e.g. caregiver relief);
- Hospitalization for surgery/procedure planned prior to study entry;
- Hospital visit less than 24 hours e.g. held for observation or treatment, but duration of stay less than 24 hours;
- Treatment at hospital or center for minor procedures (e.g. laser eye surgery).

7.1.5.4 Definition of a Suspected Unexpected Serious Adverse Reaction

A suspected unexpected serious adverse reaction (SUSAR) is a related SAE that is both serious and unexpected as assessed using the current Investigator's Brochure or Product Information.

7.1.5.5 Anticipated Serious Adverse Device Effect

An anticipated SADE is a SADE which by its nature, incidence, severity or outcome has been identified in the current version of the Investigator's Brochure or Product Information.

7.1.5.6 Unanticipated Serious Adverse Device Effect

An unanticipated SADE is a SADE which by its nature, incidence, severity or outcome has not been identified in the current version of the Investigator's Brochure or Product Information.

7.1.5.7 Device Deficiency

A device deficiency is an inadequacy of a medical device with respect to its identity, quality, durability, reliability, safety or performance. Device deficiencies include malfunctions, use errors and inadequate labelling.

7.1.5.8 Severity of Adverse Events

The investigator will make an assessment of intensity for each AE and SAE reported during the study. The assessment will be based on the investigator's clinical judgment. The severity of each AE and SAE recorded in the eCRF should be assigned to one of the following categories:

- Mild:** An AE that is easily tolerated by the subject, causes minimal discomfort and does not interfere with everyday activities.
- Moderate:** An AE that is sufficiently discomforting to interfere with normal everyday activities; intervention may be needed.
- Severe:** An AE that prevents normal everyday activities; treatment or other intervention usually needed

7.1.5.9 Relationship of Adverse Events

The investigator is obligated to assess the relationship between graded exercise and passive stretching and the occurrence of each AE/SAE. The investigator will use clinical judgment to determine the relationship. Alternative causes, such as natural history of the underlying diseases, concomitant therapy, other risk factors, and the temporal relationship of the event to the therapeutic intervention will be considered and investigated.

The causal relationship of the AE to the therapeutic intervention or study procedures should be assessed by the investigator (or medically qualified delegate) using the following classifications:

- Not Related:** In the investigator's opinion, there is not a causal relationship between the therapeutic intervention and the AE.
- Unlikely:** The temporal association between the AE and therapeutic intervention is such that the study product is not likely to have any reasonable association with the AE.
- Possible:** The AE follows a reasonable temporal sequence from the time of therapeutic intervention but could have been caused by the study subject's clinical state or other modes of therapy administered to the subject.
- Probable:** The AE follows a reasonable temporal sequence from the time of therapeutic intervention, abates upon discontinuation of the therapeutic intervention and cannot be reasonably explained by the known characteristics of the study subject's clinical state.
- Highly Probable:** The AE follows a reasonable temporal sequence from the time of therapeutic intervention, abates upon discontinuation of the therapeutic intervention and reappears when the therapeutic intervention is reintroduced.

7.1.5.10 Relationship of Adverse Events to Investigational Device

The investigator is obligated to assess the relationship between the investigational device and the occurrence of each AE/SAE. The investigator will use clinical judgment to determine the relationship. Alternative causes, such as natural history of the underlying diseases, concomitant therapy, other risk factors, and the temporal relationship of the event to the device use will be considered and investigated.

The causal relationship of the AE to the investigational device or study procedures should be assessed by the investigator (or medically qualified delegate) using the following classifications:

- Not Related: In the investigator's opinion, there is not a causal relationship between the investigational device and the AE.
- Unlikely: The temporal association between the AE and investigational device is such that the investigational device is not likely to have any reasonable association with the AE.
- Possible: The AE follows a reasonable temporal sequence from the time of use of the investigational device but could have been caused by the study subject's clinical state or other modes of therapy administered to the subject.
- Probable: The AE follows a reasonable temporal sequence from the time of use of the investigational device, and cannot be reasonably explained by the known characteristics of the study subject's clinical state.

Adverse events that have a relationship (possible or probable) to the investigational device, are termed ADEs.

